7 HANDLING OF DROPOUTS AND MISSING DATA

7.1 Dropouts

In this study, every effort is made to retain all subjects through Week 12, whether or not they are still on study medication.

For the primary endpoint (percentage of subjects remaining on spironolactone at Week 12), any subject who terminates early is defined as not having remained on spironolactone. All ITT subjects will be included in the analysis.

7.2 Missing AOBP

If the AOBP SBP is missing at a scheduled visit, the SMBP SBP for that visit will be used in analysis.

7.3 Missing Information for Adverse Events

For subjects with the missing information for adverse events, the following imputation rules will be applied:

- An adverse event with onset date equivalent to the first dosing date will be considered to be treatment-emergent unless there is evidence to conclude that it is not.
- An adverse event with missing severity will be assigned to the highest severity observed for the subject, among all events with the same preferred term; if there are no other AEs with same preferred term and non-missing severity, the adverse event will be counted as severe.
- An adverse event with missing relationship to study drug (patiromer/placebo or spironolactone) will be assigned to possible relationship (i.e. related).

7.4 Missing Dates or Partially Missing Dates

Missing or partially missing dates will be imputed conservatively for concomitant medications, procedures and adverse events (AEs). Specific rules for handling missing or partially missing dates are provided in the Appendix B.

No imputations for other missing safety data will be undertaken.

8 STATISTICAL METHODOLOGY AND STATISTICAL ANALYSES

8.1 General Considerations and Statistical Methods

Efficacy analyses will be performed by planned treatment (i.e. as randomized), and safety analyses by actual treatment received.

For continuous variables, descriptive statistics will include the number of subjects, mean, standard deviation (SD), standard error (SE), median, 25th, 75th percentiles, minimum and maximum.

For categorical variables, descriptive statistics will include frequencies and percentages in each category.

For time-to-event variables, the descriptive statistics will include the median, 95% CI, 25th/75th percentiles, minimum and maximum. Counts of events and of number censored will also be provided.

When mean change from baseline is summarized, subjects will be included in the analysis if they have both a baseline value and a post-baseline value at the time point of interest.

All statistical tests will be conducted at a two-sided alpha level of 0.05, and 95% confidence intervals will be utilized, unless otherwise stated.

Detailed statistical methods are specified in sections below.

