5.2 Per-protocol Population (PP)

The per-protocol population includes ITT subjects who have been compliant with dosing of both spironolactone and patiromer/placebo and who do not have any important protocol deviations (see Section 5.4).

Dosing compliance is defined as having taken 80-120% of the prescribed dose.

The primary and secondary endpoints will be performed using the PP Population, in addition to the ITT Population.

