6 ENDPOINTS AND VISIT WINDOWS

6.1 Efficacy Endpoints

6.1.1 Primary Efficacy Endpoint

The primary efficacy endpoint for this study is the proportion of subjects remaining on spironolactone at Week 12.

Subjects who terminate from the study early or discontinue study spironolactone prior to Week 12, for any reason, will be considered as not having remained on spironolactone until Week 12.

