6.1.2 Secondary Efficacy Endpoint

The secondary efficacy endpoint is change from Baseline in AOBP SBP at Week 12 or last available AOBP SBP prior to addition of any new BP medications or increase from any baseline BP medications.

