8.9 Efficacy Analyses

8.9.1 Primary Efficacy Analysis

The primary efficacy endpoint for this study is the proportion of subjects remaining on spironolactone at Week 12.

A subject is defined as having remained on spironolactone until Week 12 if the End of Study Treatment eCRF confirms the subject has completed the full 12-week course of study treatment and the subject had not discontinued spironolactone early. Subjects who terminate from the study early or discontinue spironolactone early, for any reason, will be defined as not having remained on spironolactone until Week 12. The number and percentage of subjects remaining on spironolactone at Week 12, and the 95% CI, will be provided by treatment group. Confidence intervals will be obtained using the exact (Clopper-Pearson) method.

The percentage of subjects remaining on spironolactone at Week 12 will be compared between treatment groups (spironolactone + patiromer versus spironolactone + placebo) using a Cochran-Mantel-Haenszel (CMH) test, at α -level 0.05. The test will be stratified by baseline potassium category (4.3 to < 4.7 mEq/L or 4.7 to 5.1 mEq/L) and Type 1 or 2 diabetes mellitus (Yes or No).

The primary analysis will be performed using the ITT and PP Populations.

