8.9.2 Secondary Efficacy Analysis

The secondary efficacy endpoint is change from Baseline in AOBP SBP at Week 12 or last available AOBP SBP on or prior to the first date of addition of any new BP medications or increases from any baseline BP medications.

Baseline AOBP is defined as the latest available AOBP on or before the date of first dose date.

Changes/additions to baseline BP medications are recorded on the Antihypertensive Medications eCRF. The earliest date of any recorded increase/addition will be compared to the date of the Week 12 AOBP, and the rules below will be applied. Note that only dates of BP medication increases/additions with start date on or before the upper limit of the Week 12 window will be considered.

- If the earliest date of BP medication increase/addition is on or after the date of the Week 12 AOBP, or there is no record of any increase/addition, the Week 12 AOBP SBP will be used for analysis.
- If the earliest date of BP medication increase/addition is prior to the Week 12 AOBP, or when the Week 12 visit should have occurred if there is no Week 12 AOBP, then the AOBP on or before and closest to the earliest date of change will be used for analysis.
- If a subject has no Week 12 AOBP and no record of any BP medication changes/additions, the subject will not be included in this analysis.

In above rules, the SMBP, if available, may be used in place of a missing AOBP at the same visit.

The secondary efficacy endpoint will be analyzed using an analysis of covariance (ANCOVA) model, with baseline AOBP SBP as a continuous covariate and factors for treatment group, baseline serum potassium (K^+ 4.3 – < 4.7 or 4.7 – 5.1 mEq/L), and Type 1 or 2 diabetes mellitus (Yes or No).

The analysis will be performed using the ITT and PP Populations. A sensitivity analysis will be performed using the last observation carried forward, when a subject has no Week 12 AOBP and no record of any BP medication changes/additions.

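### No testing order links the primary and secondary endpoints, so an SBP significance claim stays open even if the primary test fails

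*SAP*

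**What the plan says.** SAP 8.1 gives the general rule: "All statistical tests will be conducted at a two-sided alpha level of 0.05". The same sentence ends "95% confidence intervals will be utilized, unless otherwise stated", so an exception is possible but has to be written down.

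There is one endpoint at each level. SAP 6.1.1: "The primary efficacy endpoint for this study is the proportion of subjects remaining on spironolactone at Week 12". SAP 6.1.2: "The secondary efficacy endpoint is change from Baseline in AOBP SBP at Week 12 or last available AOBP SBP", the latter being the last value before antihypertensive treatment is added or increased.

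For the primary, SAP 8.9.1 repeats the level: the groups are compared "using a Cochran-Mantel-Haenszel (CMH) test, at α -level 0.05". For the secondary, SAP 8.9.2 says "The secondary efficacy endpoint will be analyzed using an analysis of covariance (ANCOVA) model" and lists the covariates. It states no alpha and no condition on the primary result, so the 8.1 default applies.

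Protocol 9.6.1 to 9.6.3 describe the same endpoints and add no order, gatekeeping or alpha split. The protocol and SAP section 1 both give the SAP precedence. Neither document contains a multiplicity section.

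**The concern.** The labels primary and secondary rank the two endpoints. They do not say what may be concluded about the second if the first is not significant. Under a blanket 0.05 rule, each test can be read alone at full alpha.

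This matters because blood pressure is not a minor endpoint here. Blood pressure control is in the trial's title and is one of the two objectives in SAP 2.1. A split result is also conceivable. Similar proportions could stay on spironolactone in the two arms while the doses reached differ, since Protocol Appendix C makes the dose increase depend on potassium. SBP might then differ while persistence does not. The status of such a result should be settled before unblinding, which SAP section 3 places after database lock.

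At stake is the error rate over the pair of claims, and the standing of an SBP result that follows a non-significant primary.

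**Working it through.** **Inputs.** Two-sided 0.05 for both tests (SAP 8.1; repeated for the primary in 8.9.1). One primary and one secondary endpoint (SAP 6.1.1, 6.1.2). 280 subjects analysed, 90% power, 20-point difference (SAP 2.3). 1:1 allocation, so 140 per arm (SAP 3). No interim efficacy analysis (SAP 4), so no alpha is spent there. Two inputs are assumptions because the documents do not give them: the component rates behind the 20 points, and the correlation between the two test statistics.

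**1. The plan's sample size.** Assume 40% versus 60%, which has the largest variance for a 20-point difference. With pooled variance under the null,

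n per arm = [1.960 × √(2 × 0.5 × 0.5) + 1.282 × √(0.4 × 0.6 + 0.6 × 0.4)]² / 0.20² = (1.386 + 0.888)² / 0.04 ≈ 129.3, so 130 per arm and 260 in total.

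The continuity correction gives (129.3 / 4) × [1 + √(1 + 4 / (129.3 × 0.20))]² ≈ 139.1, so 140 per arm and 280 in total. The stated figure is reproduced, with all of alpha 0.05 used by the primary. Without the correction, power at 280 is 92.2%.

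**2. Error over the two endpoints as the plan stands.** With both nulls true and independent tests,

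P(at least one rejection) = 1 − 0.95² = 0.0975.

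For correlated tests, take the statistics as bivariate normal with correlation ρ:

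P(at least one rejection) = 1 − P(|Z₁| < 1.96 and |Z₂| < 1.96).

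The chance that the secondary is significant and the primary is not equals this value minus 0.05.

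| Assumed ρ | At least one false rejection | Secondary significant, primary not | At least one false rejection favouring patiromer (nominal 2.5%) |
|---|---|---|---|
| 0 | 9.75% | 4.75% | 4.9% |
| 0.3 | 9.5% | 4.5% | 4.8% |
| 0.5 | 9.1% | 4.1% | 4.5% |
| 0.7 | 8.4% | 3.4% | 4.2% |
| 0.9 | 7.0% | 2.0% | 3.5% |

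Whatever the dependence, the two-sided total cannot exceed 0.05 + 0.05 = 10%.

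**3. Error under a fixed sequence.** If both nulls are true, a false claim needs the primary to reject, so the error is at most 5%. If only the primary null is true, the only possible false claim is on the primary: at most 5%. If only the secondary null is true, the only possible false claim is on the secondary, and that test must itself reject at 0.05: at most 5%. The total is therefore at most 5% in every case.

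**4. The alternative of splitting alpha.** At 0.025 for each endpoint, primary power at 280 (40% versus 60%, no continuity correction) is

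Φ{[0.20 × √140 − 2.241 × √0.5] / √0.48} = Φ(1.128) = 87.0%, down from 92.2%.

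The number needed for 90% power rises from 260 to 306. A fixed sequence takes nothing from the primary.

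**The case against.** The strongest case against is that this is a Phase 2 trial with a single primary endpoint, powered only on that endpoint. The primary inference has a 5% error rate whatever happens to the secondary. If the primary effect is real, the sequence will seldom block the SBP test, and a false SBP claim is limited to about 5% with or without an order. The order matters only when the primary fails. The blood pressure objective is also worded as a consequence of longer spironolactone use, so an SBP difference without a persistence difference would not meet it as written.

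Most of this stands and limits the weight of the point. It does not close the gap. The wording of the objective guides interpretation but is not a testing rule, and the one stated rule attaches 0.05 to the SBP test without condition.

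Three stronger readings are tempting, and the documents do not support them.

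- A reader might infer that the SAP declares both tests confirmatory, or says that an SBP claim survives a failed primary. It says neither. The claim is left open by silence plus a general default.
- A reader might take 9.75% as the error rate to expect. It requires independent tests. Protocol 1.2 expects the blood pressure difference to follow the difference in persistence, so positive correlation is more plausible and the figure is likely to be lower.
- A reader might infer from SAP 8.9.1, "The primary analysis will be performed using the ITT and PP Populations", that the deciding population is undefined. Protocol 9.6.1 names ITT for the primary and 9.6.2 names it for the secondary. SAP 5.1 puts all efficacy analyses on ITT, SAP 7.1 includes every ITT subject in the primary analysis, and SAP 5.2 makes PP supplementary: "The primary and secondary endpoints will be performed using the PP Population, in addition to the ITT Population".

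**Conclusion.** The concern holds for the secondary endpoint. The plan has no rule that ties the SBP test to the primary result, and its only general rule gives that test the full two-sided 0.05. With both nulls true, the family-wise error over the two endpoints is 9.75% under independence and about 9.1% to 7.0% for assumed correlations of 0.5 to 0.9, against at most 5% under a fixed sequence. These figures rest on two-sided tests at exactly 0.05, approximate bivariate normality, and correlations that are illustrative because neither document gives one. The excess over 5% remains across the whole range shown.

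The primary conclusion is not affected. This is a change that should be made before database lock, not a flaw that puts the main result in doubt.

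**What to change.** Add to SAP 8.1 or 8.9.2 a fixed sequence in the ITT Population:

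1. Test the primary endpoint with the CMH test of SAP 8.9.1 at two-sided 0.05.
2. Only if that test is significant, test the secondary SBP endpoint with the ANCOVA of SAP 8.9.2 at two-sided 0.05. Otherwise report the SBP estimate, interval and p-value as descriptive.
3. Treat all other efficacy p-values as nominal. This covers the PP analyses, the last-observation-carried-forward sensitivity analysis, the Week 12 SBP analyses by ANCOVA and repeated measures, the spironolactone exposure comparisons and log-rank test, and the interaction tests for the seven subgroups in SAP 8.9.4.

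The cost is a short SAP amendment. Primary alpha (0.05), the stated 90% power and the 280 analysed do not change, and no further subjects are needed. The one real downside is that a true SBP effect could not be claimed formally if the primary fails.

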8.2 Subject Disposition

The number and percentage of subjects randomized, subjects who receive study drug, and subjects who complete study (or are terminated early) will be summarized by treatment group and overall. The number and percentage of subjects terminating from the study early will be presented by reason. The ITT, PP, and Safety Populations will also be summarized by treatment group and overall. If populations do not differ (e.g. ITT and Safety Populations) then the summary will be presented only once.

In addition, the number and percentage of subjects who signed informed consent, screen failures and screen failure reasons will be summarized.

Listings of subject disposition and screening will be provided.

8.3 Demographics and Baseline Characteristics

Demographics and baseline characteristics will be summarized for the ITT, PP and Safety Populations (if they differ from ITT), by treatment group and overall.

The summary of demographic information will include age, sex, race and ethnicity. The summary of patient characteristics at baseline will include, but is not limited to, weight, height, BMI, baseline medical history (including chronic kidney disease, diabetes types, hypertension, heart failure including NYHA class, ejection fraction (EF), myocardial infarction, baseline serum potassium and eGFR).

Listings of demographics and baseline characteristics will be provided.

8.4 Medical History

General medical history will be coded in accordance with MedDRA 18.1 and will be summarized by body system (or procedure), for each treatment group and overall.

A listing of general medical history will be provided.

8.5 Prior and Concomitant Medications

All prior and concomitant medications will be coded using the current version of the World Health Organization Drug dictionary (WHO Drug Sep2016).

Prior medications are defined as medications with start date before the date of first dose of study medication. Concomitant medications are those taken during the study period, and are defined as medications with start date on or before the date of last dose of study medication and end date on or after the date of first dose of study medication, or no end date.

Prior and concomitant medications will be separately summarized by treatment and overall. Additional summaries will be provided for concomitant medications of interest, including all antihypertensive agents and medications for diabetes mellitus (Type 1 or 2). Summaries will be presented by treatment group and overall.

Listings of all prior and concomitant medications will be provided.

8.6 Exposure to Study Drug

Exposure to study drug will be summarized separately for spironolactone and patiromer/placebo. Summaries will be provided, by treatment group, for:

- Duration: calculated as [last dose date]-[first dose date]+1.
- Total dose: calculated for each subject as the total dosage received
- Mean daily dose: calculated for each subject as the total dose divided by the duration of study drug exposure
- Number and type of titrations (up or down)

In addition, for patiromer/placebo, the number of non-zero dose days will be summarized.

Separate listings will be provided for spironolactone and patiromer/placebo exposure.

8.7 Compliance

Study drug compliance will be assessed separately for spironolactone and patiromer/placebo. Summaries will be presented by treatment group.

Dose compliance will be derived from the total dose of study drug taken by a subject divided by the prescribed total dose over the treatment period, multiplied by 100.

Descriptive statistics will be provided for dose compliance. In addition, counts (%) will be provided for compliance categories 80-120%, < 80%, and > 120%.

A listing of compliance for each study drug by subject will be provided.

8.8 Protocol Deviations

The number and percentage of subjects with protocol deviations will be summarized by category of deviation, for each treatment group and overall. A listing of important protocol deviations will be provided.

8.9 Efficacy Analyses

8.9.1 Primary Efficacy Analysis

The primary efficacy endpoint for this study is the proportion of subjects remaining on spironolactone at Week 12.

A subject is defined as having remained on spironolactone until Week 12 if the End of Study Treatment eCRF confirms the subject has completed the full 12-week course of study treatment and the subject had not discontinued spironolactone early. Subjects who terminate from the study early or discontinue spironolactone early, for any reason, will be defined as not having remained on spironolactone until Week 12. The number and percentage of subjects remaining on spironolactone at Week 12, and the 95% CI, will be provided by treatment group. Confidence intervals will be obtained using the exact (Clopper-Pearson) method.

The percentage of subjects remaining on spironolactone at Week 12 will be compared between treatment groups (spironolactone + patiromer versus spironolactone + placebo) using a Cochran-Mantel-Haenszel (CMH) test, at α -level 0.05. The test will be stratified by baseline potassium category (4.3 to < 4.7 mEq/L or 4.7 to 5.1 mEq/L) and Type 1 or 2 diabetes mellitus (Yes or No).

The primary analysis will be performed using the ITT and PP Populations.

8.9.2 Secondary Efficacy Analysis

The secondary efficacy endpoint is change from Baseline in AOBP SBP at Week 12 or last available AOBP SBP on or prior to the first date of addition of any new BP medications or increases from any baseline BP medications.

Baseline AOBP is defined as the latest available AOBP on or before the date of first dose date.

Changes/additions to baseline BP medications are recorded on the Antihypertensive Medications eCRF. The earliest date of any recorded increase/addition will be compared to the date of the Week 12 AOBP, and the rules below will be applied. Note that only dates of BP medication increases/additions with start date on or before the upper limit of the Week 12 window will be considered.

- If the earliest date of BP medication increase/addition is on or after the date of the Week 12 AOBP, or there is no record of any increase/addition, the Week 12 AOBP SBP will be used for analysis.
- If the earliest date of BP medication increase/addition is prior to the Week 12 AOBP, or when the Week 12 visit should have occurred if there is no Week 12 AOBP, then the AOBP on or before and closest to the earliest date of change will be used for analysis.
- If a subject has no Week 12 AOBP and no record of any BP medication changes/additions, the subject will not be included in this analysis.

In above rules, the SMBP, if available, may be used in place of a missing AOBP at the same visit.

The secondary efficacy endpoint will be analyzed using an analysis of covariance (ANCOVA) model, with baseline AOBP SBP as a continuous covariate and factors for treatment group, baseline serum potassium (K^+ 4.3 – < 4.7 or 4.7 – 5.1 mEq/L), and Type 1 or 2 diabetes mellitus (Yes or No).

The analysis will be performed using the ITT and PP Populations. A sensitivity analysis will be performed using the last observation carried forward, when a subject has no Week 12 AOBP and no record of any BP medication changes/additions.

